COMIRB Protocol

**COLORADO MULTIPLE INSTITUTIONAL REVIEW
BOARD
[name] [contact]
[contact]**

Protocol #: 18-1854

Project Title: Evaluation of pancreatic cystic lesions via EUS-guided fine needle aspiration with and without micro forceps biopsies: A randomized controlled study

Principal Investigator: [name]

Version Date: February 5, 2021

I. Hypothesis: Evaluation of pancreatic cystic lesions using endoscopic ultrasound with fine needle aspiration (EUS-FNA) of cyst fluid and microforceps biopsies (EUS-MFB) has greater diagnostic yield and equivalent safety profile compared to EUS with fine needle aspiration (EUS-FNA) alone.

Specific Aims: To prospectively compare the efficacy and safety of EUS evaluation of pancreatic cystic lesions with 1) EUS-FNA plus MFB versus 2) EUS-FNA alone, in a randomized controlled study.

II. Background and Significance:

Pancreatic cystic lesions (PCLs) are a common incidental finding in cross sectional imaging (up to 27% on CT scan and 41% on MRI¹) and pose a management challenge to physicians. According to society guidelines,²⁻⁴ PCLs with specific features should prompt additional workup with endoscopic ultrasound (EUS) for cyst characterization as well as cyst sampling. This can help determine if the cyst is mucinous or non-mucinous which has implications for its malignant potential. Cyst fluid has traditionally been sampled using EUS with fine needle aspiration (EUS-FNA) and sent for fluid analysis and cytology. However, despite use of a cyst fluid carcinoembryonic antigen (CEA) level cutoff⁵ of 192 ng/mL and cytology, accuracy of diagnosis for PCLs is poor. As the spectrum ranges from benign to high risk for neoplasm, precise diagnosis is critical.

More recently, the adjunctive use of the Moray® through the needle microforceps biopsy (EUS-MFB) has shown promise for diagnosis of PCLs.⁶ This technology utilizes a microforceps through a 19-gauge

needle to biopsy the cyst wall for histology, in addition to collecting cyst fluid for CEA level and cytology. Only a few small retrospective reports have been published regarding the use of MFB.

D. Innovation:

Pancreatic cysts continue to pose a management dilemma for practicing clinicians, especially with the increased use of radiologic imaging modalities identifying incidental pancreatic cystic lesions with higher frequency. This leads to patient anxiety and increased costs due to radiologic surveillance and even surgery. The results of this study will hopefully help increase diagnostic yield by obtaining a histopathologic diagnosis of these PCLs, and potentially affect practice patterns of gastroenterologists and the endoscopic community, specifically those physicians who perform EUS in these patients. Furthermore, the results will help determine whether there is reason to continue this line of research to obtain a definite histologic tissue diagnosis of PCLs.

III. Preliminary Studies/Progress Report:

We recently published our retrospective series of 27 patients using EUS-MFB for evaluation of PCLs and reported technical success of 100% and obtained a pathological diagnosis in 24 of 27 cases (yield 88.9%) with MFB. In 7 patients (26%), microforceps biopsy results drastically changed the diagnosis, providing diagnoses otherwise not suggested by cytology or cyst fluid CEA levels. However, cytology provided a diagnosis of mucinous cyst in 4 cases (14.8%) not detected by microforceps biopsies. No adverse events were noted.

Other small retrospective studies have shown that cyst fluid analysis via FNA is comparable to MFB for distinguishing mucinous from non-mucinous cysts, but MFB is better at diagnosing the specific cyst subtype.^{8,9} However, prospective data on the use and safety of MFB for PCLs is lacking.

IV. Research Methods

The study will be performed at 3 participating sites:

- (1) University of Colorado Hospital-Anschutz Medical Campus (UCH-AMC), Aurora, CO (Primary site)
- (2) Mt. Sinai Medical Center, New York, NY
- (3) University of California, Irvine, CA.

The study will be conducted after obtaining approval from the Institutional Review Board at all sites.

A. Outcome Measure(s):

Primary Outcomes:

A. Compare the efficacy and safety of EUS-FNA plus MFB, with EUS-FNA alone for evaluation of PCLs

Definitions:

A. Efficacy will be defined as technical and clinical success in performing MFB during EUS evaluation of PCLs.

(1) Technical success will be defined as the ability to puncture the cyst with the FNA needle under EUS guidance, advance the micro forceps into the cyst to perform cyst biopsies and obtain a visible tissue fragment.

(2) Clinical success will be defined as the ability to obtain a pathologic tissue diagnosis of the PCL with MFB. Based on prior experience, expected diagnoses include pseudocyst, serous cystadenoma, mucinous cyst (mucinous cystic neoplasm, intra-ductal papillary mucinous neoplasm), adenocarcinoma, and neuroendocrine tumor, to name a few.

B. Compare safety of EUS-FNA plus MFB with that of EUS-FNA by recording adverse events per published ASGE criteria (10).

Secondary Outcomes:

A. Technical ease in performing FNA and MFB:

(1) Ease of passage of FNA needle

(2) Ease of passage of Micro Forceps

(3) Ease of EUS visualization of Micro Forceps

Technical ease will be scored on a predetermined 5-point Likert scale (1 = best, 5 = worst)

B. Time taken for FNA and time for MFB

B. Description of Population to be Enrolled:

Inclusion criteria:

- Adult patients >18 years old
- Cysts > 20 mm in size deemed appropriate for FNA by the endoscopist, based on clinical presentation, radiologic imaging features, associated solid mass or nodules, and patient anxiety about the diagnosis

Exclusion criteria:

- Age <18 years
- Inability to provide informed consent
- Thrombocytopenia (Platelets < 50,000) or coagulopathy (INR > 1.8)

- Pregnancy
- Post-surgical anatomy where the cyst is not accessible for FNA
- EUS findings suggesting that cyst FNA would be unsafe (e.g. intervening blood vessels)
- EUS appearance suggesting FNA is not indicated (e.g. cyst smaller than prior radiologic imaging, cyst not seen, EUS suggestive of serous cystadenoma)

C. Study Design and Research Methods

Patients will be provided the necessary information regarding the study and consent will be obtained either in person and/or electronically through medical records depending on specific site IRB approval guidelines. Patients will be randomized to intervention 1) EUS-FNA plus MFB or 2) EUS-FNA alone

D. Description, Risks and Justification of Procedures and Data Collection Tools:

Patients will be enrolled in this study when evaluated in GI clinics, hospital wards, and endoscopy suites. Consent for the study will be obtained either in person, by the interventional endoscopist who will be performing the procedure or by the research assistant/ study coordinator or electronically through medical records depending on specific site IRB approval guidelines. All UCH interventional endoscopists who perform EUS will participate in the study. All participating investigators are experienced interventional endoscopists proficient in EUS. Initial evaluation of patients will include collection of data on demographics, history, physical examination and pertinent radiologic, laboratory, and endoscopic data, and prior management/therapies. Details of previous endoscopic and surgical evaluation along with histopathology data will be documented, as needed for clinical care.

After obtaining informed consent, subjects will undergo EUS per clinical protocol. All procedure-related clinical decisions and interventions will be dictated by the performing physician as he or she sees fit. Once the pancreatic cystic lesion is seen and assessed by EUS, randomization will be performed after determination by the endoscopist and research coordinator that the patient meets inclusion criteria and does not have exclusion criteria.

A pancreatic cyst with high risk stigmata (presence of dilated main pancreatic duct > 10 mm, mural nodule or associated solid mass) would be referred for surgical resection based on patient's clinical status, irrespective of cyst fluid analysis/cyto/pathology. Cysts without high risk stigmata are followed with radiologic surveillance imaging in 1-3 years

Procedure description:

Prophylactic antibiotics (Ampicillin-Sulbactam 3 g or Ciprofloxacin 500 mg intravenous) will be administered to all patients prior to needle puncture of the cyst, and for 3-5 days post procedure (Amoxicillin-Clavulanate or Ciprofloxacin orally) as per routine standard of care. A detailed endosonographic examination of the cyst will be performed using a curvilinear array echoendoscope (Olympus America, Center Valley, PA) as per routine clinical care. Careful evaluation will be performed for cyst location, size, presence of mural nodule, associated solid mass, and communication with the main pancreatic duct. Patients will then be randomized by a computer-generated algorithm to EUS-FNA plus MFB (group 1) or EUS-FNA alone (group 2). Histological diagnosis is considered a gold standard and a positive MFB diagnosis is considered a true diagnosis. Please note that currently we have been performing EUS-FNA and MFB for pancreatic cysts as part of routine clinical care and this is NOT considered experimental. This procedure does not have negative implications for insurance coverage, patient charges, and hence will not affect our budget. We will perform the procedure for patient care irrespective of the study.

(1) EUS-MFB plus FNA group:

The cyst will be punctured using a 19-G EUS-FNA needle with a stylet. A transgastric approach will be used for PCLs located in body/tail region, and a transduodenal approach for PCLs in the head/neck region, or as determined by the endoscopist. The stylet will be removed and the wall of the cyst biopsied using the micro forceps passed through the 19 G needle under direct EUS visualization. A minimum of 4 cyst wall biopsies will be obtained to procure at least 4 visible tissue fragments. Cyst fluid will be aspirated and sent for CEA and cytology.

(2) EUS-FNA alone group:

The cyst will be punctured using an EUS-FNA needle with a stylet. A transgastric approach will be used for PCLs located in body/tail region, and a transduodenal approach for PCLs in the head/neck region, or as determined by the endoscopist. The stylet will be removed, and cyst fluid will be aspirated and sent for CEA, and cytology.

UCH cytopathologists and pathologists experienced in pancreatic cytology and pathology will evaluate all cytology and micro forceps biopsy specimens per standard clinical care. Clinical follow-up will be obtained as per routine clinical care.

Use of fine needle aspiration as well as micro forceps biopsy for pancreatic cysts is safe with low rates of adverse events. Therefore, the risk to the patient is minimal. Additionally, accurate diagnosis is critical, as pancreatic cysts range from benign to malignant. Thus, comparing two interventions to evaluate cystic lesions to determine the optimal modality for diagnosis is justified.

Data collection will be carried out by the study team under the direction of the principal investigator. A REDCap database will be used to store clinical data information for subjects who consent to participate. This will serve as a clinical data repository for subject data. Clinical data will be extracted by the investigators or PRA from medical chart review. Access to the REDCap database will be granted by the study team, sometimes in limited fashion (e.g. no access to identifiers), to research staff and to co-investigators when needed. The final responsibility for the completeness and accuracy of all study data will belong to the principal investigator.

The study team will reach out to the subject at two different points post procedure.
1) Up to 72 hours post-procedure to collect data on the first 24 hours and
2) At day 30 to collect data AE data from the previous 30 days. Adverse events will be recorded per published ASGE criteria (10). The PI will continuously review local AEs and a safety officer not directly participating in the endoscopic procedures will review adverse events every 6 months. The PI will review serious device related events within 48 hours of the lead site becoming aware of the event. No serious adverse events were seen in our initial study (7) and in the study by Basar et al (9). Potential adverse events after these procedures include bleeding, perforation, infection, pancreatitis, and sedation-related complications, to name a few. Based on prior experience (7, 9) we do not expect a high rate of adverse events. Hence, we do not anticipate the need for an interim analysis.

E. Potential Scientific Problems: N/A

F. Data Analysis Plan:

The primary outcome of the study is to compare the diagnostic yield of the efficacy and safety of EUS-FNA plus EUS-MFB, with EUS-FNA alone for evaluation of PCLs.

Descriptive statistics will be used to summarize the data. Continuous variables will be expressed as mean \pm standard deviation and categorical variables will be mentioned in percentages. T-test for continuous variables and Fisher's exact test or chi-square test for categorical variables will be used as appropriate.

Sample size calculation was performed as follows: to power the study to detect a 20% difference in efficacy would require enrollment of 76 patients in each group. However, after accounting for screen failures, technical failures in performing FNA/MFB based on actual findings during EUS where FNA/MFB would not be possible, patient drop out and loss to follow-up, we estimate 25% more patients would need to be included i.e. 102 patients would be needed in each group to get 76 patients in each arm who would actually get FNA/MFB. Statistical

analysis will be independently performed by intention to treat analysis by the University of Colorado Center for Innovative Design and Analysis, not by the PI

G. Summarize Knowledge to be Gained:

Most of the current data on evaluation of PCLs emphasizes the limitations in cyst sampling techniques and technologies. We are still far from being able to accurately diagnose many of these lesions. We have recently published results showing the safety and efficacy of the microforceps biopsy in a retrospective cohort, and much of the other data on MFB comes from case reports and small retrospective case series. There has never been a head to head trial comparing these two interventions. Additionally, there is no “standard” intervention and approach to PCLs is largely influenced by practice patterns among physicians as well as equipment availability. This is a prospective randomized controlled study that will help answer the question on which approach lends itself to more technical success and higher diagnostic yield while monitoring safety profile.

H. References:

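### The hypothesis claims equivalent safety, but the plan offers only a test of difference for adverse events, with no margin or confidence interval

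*Combined protocol and SAP*

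**What the plan says.** The hypothesis in Section I has two halves: the combined procedure "has greater diagnostic yield and equivalent safety profile compared to EUS with fine needle aspiration (EUS-FNA) alone". The Specific Aims that follow are more neutral: "To prospectively compare the efficacy and safety of EUS evaluation of pancreatic cystic lesions".

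Section IV.A puts safety under Primary Outcomes ("Compare the efficacy and safety of EUS-FNA plus MFB, with EUS-FNA alone for evaluation of PCLs"), and definition B there reads "Compare safety of EUS-FNA plus MFB with that of EUS-FNA by recording adverse events", using the ASGE criteria. Section IV.F again names safety in the primary outcome.

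Section IV.F holds all the statistical methods: means with standard deviations, percentages, the t-test, and Fisher's exact or chi-square test as appropriate. The sample size is 76 per group for a 20% difference in efficacy, raised to 102 per group for failures and losses. The analysis is by intention to treat.

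On event rates, Section III says of the 27-patient series "No adverse events were noted". Section IV.D expects no high rate but gives no figure. It sets two contacts after the procedure, the second described as "At day 30 to collect data AE data from the previous 30 days".

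**The concern.** A test of difference asks whether the data contradict equal rates. Failing to reject may mean that the rates are close, or only that there were too few events to tell. Claiming equivalence needs a largest acceptable difference stated in advance and an interval that lies within it. The plan has neither.

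The protocol expects few adverse events, which is where a non-significant result says least. Nothing in the plan says such a result will be read as equivalence, but nothing rules that out, and the hypothesis invites it. Section III itself says prospective safety data on MFB are lacking, so readers will want to know how much added risk the results leave open. A p-value does not tell them.

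**Working it through.** **Inputs from the documents.** Section IV.F: 76 per arm expected to undergo the procedure, and 102 per arm included. Section III: 0 adverse events in 27 patients. Alpha is not stated; two-sided 5% is assumed throughout. No adverse event rate or margin is given, so those used in steps 4 to 6 are assumptions.

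**1. The plan's own figures.** 76/(1 - 0.25) = 101.3, rounded up to 102, as stated. The 76 cannot be uniquely reproduced, because base rates, alpha and power are missing. It is attainable: 68% v 88% with continuity correction, two-sided 5% and 80% power gives 76. Both figures concern efficacy; there is no safety figure to reproduce. 102 is an upper bound for the number randomized, since Section IV.D says "randomization will be performed after determination by the endoscopist and research coordinator that the patient meets inclusion criteria", which should remove most screen failures first.

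**2. Smallest splits that reach p ≤ 0.05 (no assumed rate needed).**

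| Lower arm | Fisher, 76 per arm | Chi-square (uncorrected), 76 per arm |
|---|---|---|
| 0 events | 6 v 0 (p = 0.028) | 4 v 0 (p = 0.043) |
| 1 event | 8 v 1 (p = 0.034) | 7 v 1 (p = 0.029) |
| 2 events | 10 v 2 (p = 0.031) | 8 v 2 (p = 0.0496) |

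At 102 per arm the Fisher splits are the same.

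**3. What a non-significant result leaves open (no assumed rate needed).** The Newcombe interval combines the Wilson limits (l, u) of each arm:

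- lower = d - √[(p₁ - l₁)² + (u₂ - p₂)²]
- upper = d + √[(u₁ - p₁)² + (p₂ - l₂)²]

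where d = p₁ - p₂.

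- 3 v 0 at 76 per arm: p₁ = 3.95%, Wilson limits 1.35% to 10.97%; p₂ = 0, upper limit 4.81%. Lower = 3.95 - √(2.60² + 4.81²) = -1.5. Upper = 3.95 + √(7.03² + 0²) = 11.0. Fisher p = 0.245, chi-square p = 0.080.
- 3 v 0 at 102 per arm: -1.2 to +8.3 points.
- 0 v 0: ±4.8 points at 76 per arm, ±3.6 at 102.

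**4. Probability of a non-significant test under assumed true rates** (exact binomial enumeration).

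| FNA v FNA plus MFB | Fisher, 76 | Fisher, 102 | Chi-square, 76 | Chi-square, 102 |
|---|---|---|---|---|
| 2% v 6% | 90% | 82% | 77% | 72% |
| 2% v 8% | 76% | 62% | 60% | 50% |
| 2% v 10% | 59% | 40% | 42% | 30% |

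The 27-patient series does not exclude such MFB rates: the exact two-sided 95% upper limit for 0/27 is 1 - 0.025^(1/27) = 12.8%.

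**5. Precision the trial can offer.** Expected Newcombe half-width if both arms share the same assumed rate:

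| Rate | 76 per arm | 102 per arm |
|---|---|---|
| 1% | 5.6 points | 4.4 points |
| 2% | 6.3 points | 5.1 points |
| 5% | 7.9 points | 6.7 points |

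**6. If equivalence were kept.** Two one-sided 5% tests with no true difference and 80% power need n = 2p(1 - p)(1.645 + 1.282)²/margin² per arm. For p = 2% and a 5-point margin: 0.0392 × 8.57/0.0025 gives 135. For p = 5% it is 326. With a 10-point margin the numbers are 34 and 82. These are normal approximations and rough at such low rates.

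**The case against.** The strongest reply is that this turns on one word. The aims and outcomes speak of comparing, and Section IV.G describes safety as something monitored while yield is assessed, so *equivalent* may be loose wording. No trial decision in the documents depends on the safety test; adverse events go to the principal investigator and a safety officer. Percentages by arm are planned, so an interval could be calculated afterwards from the same data.

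Most of that is fair, and it limits the seriousness of the point. It does not remove the mismatch, because the word sits in the trial's only stated hypothesis and safety is listed as primary. A later interval would show the uncertainty, but without a margin set beforehand it could not confirm equivalence.

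Three narrower objections also have force:

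- With so few events most analysts would choose Fisher's test (the expected count at 4 v 0 is 2 per arm), so the chi-square columns mainly show that the conclusion does not depend on the choice.
- The assumed rates have no anchor in the documents, and each implies at least a threefold risk. Steps 2 and 3 do not use them.
- Section IV.D also cites a second study without serious adverse events. Its size is not given, and serious events are only part of the endpoint.

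**Conclusion.** The concern holds. Followed as written, the plan cannot support its claim of equivalent safety: it has no margin, no interval and no safety sizing, and its only applicable test addresses a different question. Without assuming any event rate, a non-significant 3 v 0 result at 76 per arm is compatible with an added risk of up to 11.0 points, and zero events in both arms with up to 4.8 points (3.6 at 102). The 90% chance of missing a 2% v 6% difference with Fisher's test depends on those assumed rates. All figures assume two-sided 5% tests or 95% intervals. The efficacy comparison and the conduct of the trial are unaffected. This should be corrected, and rewording with a planned interval is enough to do it.

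**What to change.** **Section I.** Replace the equivalence wording with an aim to estimate the between-arm difference in adverse event proportion.

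**Section IV.F.**

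- Make the difference in 30-day ASGE-defined adverse event proportion, with a two-sided 95% interval suited to rare events (Newcombe, for example), the main safety analysis.
- State that a non-significant test will not be read as equivalence.
- Report the interval with equal prominence in all randomized patients, which keeps the randomized comparison, and in those whose cyst was punctured, which avoids diluting an added MFB risk. In the extreme case where only 76 of 102 per arm are punctured and events arise only in them, a 4.0-point difference shrinks to 4.0 × 76/102 = 3.0 points among all randomized.
- Report by arm how many lack day-30 contact and how they enter the denominator. Section IV.D already provides that "Clinical data will be extracted by the investigators or PRA from medical chart review", so they could be counted with events found there, then excluded in a repeat analysis.
- Give the expected interval width over a stated range of event rates, as in step 5.

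If an equivalence or non-inferiority claim is kept, state and justify a margin in advance, judge it by the confidence limit or limits in both analysis sets, and report power at the planned size.

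**Cost.** A wording change, one interval in two analysis sets and a short rule for missing contacts; no extra patients. The safety claim becomes more modest. Keeping equivalence costs more: judged by the 95% Newcombe interval, even zero events in both arms could not meet a margin tighter than 4.8 points at 76 per arm, or 3.6 at 102.

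### Primary efficacy compares the two arms but is defined only as success with MFB, which no FNA-alone patient treated as assigned can achieve

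*Combined protocol and SAP*

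**What the plan says.** Section IV.A sets the primary outcome as a comparison between arms: "Compare the efficacy and safety of EUS-FNA plus MFB, with EUS-FNA alone for evaluation of PCLs". The definition beneath it reads "Efficacy will be defined as technical and clinical success in performing MFB during EUS evaluation of PCLs". It has two components, and both need the forceps:

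- Technical success requires the operator to puncture the cyst and then "advance the micro forceps into the cyst to perform cyst biopsies and obtain a visible tissue fragment".
- For the second component, "Clinical success will be defined as the ability to obtain a pathologic tissue diagnosis of the PCL with MFB".

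Section IV.D describes the FNA-alone procedure as follows: "The stylet will be removed, and cyst fluid will be aspirated and sent for CEA, and cytology". No biopsy is part of that arm. The same section states that "Histological diagnosis is considered a gold standard and a positive MFB diagnosis is considered a true diagnosis" and gives no matching rule for cytology or CEA.

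The Hypothesis (section I) and the Data Analysis Plan (section IV.F) speak of diagnostic yield. The term is not defined as a trial endpoint. Its only operational use is in section III, for the pilot's MFB result of 24 of 27 (88.9%). The CEA cut-off of 192 ng/mL appears only in the Background. Section IV.F sizes the trial at 76 per group for a 20% difference in efficacy, inflated to 102, with intention-to-treat analysis. It does not give alpha, sidedness, power or either arm's rate.

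**The concern.** A randomised comparison needs an outcome that can be observed in both arms under the same rule. Here the outcome is success of the experimental device, so the control arm scores zero if the protocol is followed. A significant result would show that MFB can be performed and read. It would say nothing about what FNA alone yields, which is the comparator in the hypothesis.

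If diagnostic yield is what was meant, the risk moves to the unwritten control-arm rule. Section III reports that FNA fluid analysis performs similarly to MFB for separating mucinous from non-mucinous cysts, while MFB does better on specific subtype. The same patients could therefore show little difference on one definition and a clear one on the other. If the choice is made after results are visible, the primary conclusion is open to selection.

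Group 1 is affected too. It is randomised to FNA plus MFB but scored on MFB alone, so a patient diagnosed only by cytology counts as a failure.

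**Working it through.** **1. Inputs.** From the protocol: 76 and 102 per arm and a 20% difference (IV.F); pilot MFB diagnosis in 24/27, and 4 mucinous diagnoses by cytology that MFB did not detect (III). Assumed, because not stated: two-sided alpha 0.05, 80% power, and an absolute difference of 20 points.

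**2. The plan's own figures.** The inflation reproduces: 76 / (1 − 0.25) = 101.3, rounded up to 102. The 76 cannot be derived from what is stated, so it can only be matched under assumptions (step 5).

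**3. Literal reading, patients treated as assigned.** The control count is 0. For 6 against 0 at 76 per arm, the two-sided Fisher p = 2 × C(76,6) / C(152,6) = 0.028. For 5 against 0 it is 0.058. At 102 per arm the values are 0.029 and 0.059. Six successes is 6/76 = 7.9%. The chance of 6 or more in Group 1, from the binomial distribution:

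| True MFB yield | 76 per arm | 102 per arm |
|---|---|---|
| 10% | 78% | 95% |
| 20% | 99.9% | over 99.9% |

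**4. Literal reading with MFB given off assignment.** Section IV.D says "All procedure-related clinical decisions and interventions will be dictated by the performing physician as he or she sees fit" and "We will perform the procedure for patient care irrespective of the study", so MFB in Group 2 is not ruled out. Under intention to treat, those would be Group 2's only possible successes. With 5/76 (6.6%) there, 14/76 (18.4%) in Group 1 is enough (p = 0.048). At the pilot rate Group 1 would have 0.889 × 76 ≈ 68 successes. Group 2 could then reach 57/76 (75%) before significance is lost (p = 0.032; 58/76 gives 0.051). These are boundary cases, not forecasts.

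**5. Intended reading: can the FNA rate be recovered from 76?** The pooled formula without continuity correction is

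n = [z₀.₉₇₅ √(2p̄(1 − p̄)) + z₀.₈₀ √(p₁(1 − p₁) + p₂(1 − p₂))]² / (p₂ − p₁)².

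For 16.5% vs 36.5%, p̄ = 0.265, and n = (1.960 × 0.6241 + 0.8416 × 0.6079)² / 0.04 = 75.2, so 76. For 63.5% vs 83.5% the terms are the same by symmetry about 50%, so n is again 76. With continuity correction, 12% vs 32% and 68% vs 88% both give 76. For a 20-point difference, a control rate p and its mirror 0.80 − p always need the same n, so the sample size alone cannot identify the rate. A zero control rate needs 35 per arm at these settings. It reaches about 76 only with unusual choices, such as 78 at 99% power.

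**6. Power with an endpoint both arms can reach** (two-sided 0.05, same normal approximation):

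| Assumed FNA alone vs FNA plus MFB | 76 per arm | 102 per arm |
|---|---|---|
| 40% vs 60% | 70% | 82% |
| 60% vs 80% | 77% | 88% |
| 68.9% vs 88.9% (pilot MFB rate less 20 points) | 86% | 94% |

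If 102 per arm are randomised and 26 of them have no specimen and count as no diagnosis, 40% becomes 0.40 × 76/102 = 29.8% and 60% becomes 44.7%. Power is then 60%. Starting from 68.9% vs 88.9% it is 58%. This is the extreme case: the inflation also covers screen failures, and randomisation follows EUS assessment.

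**7. Group 1 under-count in the pilot.** Patients without an MFB diagnosis number 27 − 24 = 3, so at most 3/27 (11.1%) could have been diagnosed by cytology alone, and possibly none. Cytology called 4 mucinous cysts that MFB did not detect. Since 4 exceeds 3, at least one of those patients had a different MFB diagnosis, so discordant results do occur.

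**The case against.** The best defence is that no one would run the literal test. The hypothesis of greater yield and the 20% difference both point to a non-zero FNA rate, and some elements of a common endpoint exist: expected diagnoses are listed in IV.A, a CEA cut-off is in the Background, and MFB-positive results are declared true in IV.D. That is fair as to intent. It does not supply a rule. The list of diagnoses is open-ended and attached to MFB, the cut-off is never made an endpoint criterion, and cytology has no counterpart to the MFB rule. Independent, intention-to-treat analysis does not fill the gap, because the analyst still has to be told what a control-arm success is.

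Four narrower points have substance:

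- The off-assignment sentences sit among text on routine care and budget and do not provide for MFB in Group 2. They leave it possible, and the finding does not depend on it.
- A 68% vs 88% reconstruction of the 76 is plausible because it is close to the pilot rate. It is unstated and not unique.
- 40% vs 60% is the least favourable setting for a 20-point difference, so poor power is not established.
- Giving Group 1 an additional test cannot lower its any-diagnosis yield, so a shared endpoint does not remove that advantage. This is inherent in asking what MFB adds to FNA, and should be acknowledged when results are reported.

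**Conclusion.** The concern holds and should be resolved before any outcome data are reviewed. As written, the primary efficacy endpoint has no usable definition in the control arm. That conclusion comes from the text alone and needs no assumed rates. Taken literally, 6 successes against 0 at 76 per arm is significant. Taken as intended, the control-arm rule is absent and cannot be inferred from the sample size. The power figures rest on the assumed alpha, sidedness and rates, and show a range rather than a shortfall. The safety comparison by ASGE criteria is defined for both arms and stands.

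**What to change.** Replace technical and clinical success with MFB, as the compared endpoint, by one endpoint that applies to both arms: the proportion of randomised patients with a cyst diagnosis from a pre-listed set. Use all specimens obtained (CEA and cytology in both arms, plus MFB in Group 1), analyse by randomised arm, and count a randomised patient with no specimen as having no diagnosis.

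Before any outcome data are reviewed, the sponsor should fix in writing:

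- (a) whether the primary endpoint is mucinous versus non-mucinous or specific subtype, with the other secondary;
- (b) whether and how CEA values above and below 192 ng/mL count as a diagnosis;
- (c) how discordant cytology and MFB results are classified.

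Report MFB technical and clinical success descriptively in Group 1 only. Report any off-assignment MFB in Group 2, with a sensitivity analysis that excludes its results. Use the same endpoint wording in the Hypothesis, section IV.A and section IV.F. Restate the sample-size basis with alpha, sidedness, assumed FNA rate, absolute or relative difference, and the power delivered at the planned numbers, without enlarging the trial.

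The cost is a protocol amendment to the wording of those sections. The specimens and results are already collected, so no procedures or patients are added. The price is candour about power, which may be less favourable than the plan implies: 60% to 82% at an assumed 40% vs 60%, depending on how many of the 102 per arm are randomised and sampled.
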